3.5.3.4 Exposure adjusted analysis

Exposure adjusted incidence rate of ARIA-E events will be summarized based on safety MRI data for the placebo-controlled and LTE active treatment period. The exposure adjusted follow-up time is from the first active dose until the initial occurrence of ARIA-E for those who experienced ARIA-E, and until the end of follow-up for those who did not. Since ARIA is an MRI finding, the day of the last MRI assessment in the placebo-controlled and LTE active treatment period will be used as the end of follow-up for those who didn't experience the event.

Study drug administration information prior to first ARIA-E onset will be summarized for ARIA-E subjects for the placebo-controlled and LTE active treatment period, including number of total infusions, number of infusions at each dose level (placebo, 1 mg/kg, 3 mg/kg, 6 mg/kg and 10 mg/kg), dose level of the last infusion, maximum dose level received, and cumulative dose as a continuous variable.

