4.5.3.4 Exposure adjusted analysis

Exposure adjusted incidence rate of ARIA-E events will be summarized based on safety MRI data. The exposure adjusted follow-up time is from the first dose until the initial occurrence of ARIA-E for those who experienced ARIA-E, and until the end of follow-up for those who did not. Since ARIA is an MRI finding, the day of the last MRI assessment in the placebo-controlled period will be used as the end of follow-up for those who didn't experience the event.

Study drug administration information prior to first ARIA-E onset will be summarized for ARIA-E subjects, including number of total infusions, number of infusions at each dose level (placebo, 1 mg/kg, 3 mg/kg, 6 mg/kg and 10 mg/kg), dose level of the last infusion, maximum dose level received, and cumulative dose as a continuous variable.

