3.1.2 Analyses period

Depending on the purpose, different analyses will be conducted on the following study periods:

1. LTE period. Only data in the LTE period will be included in these analyses. For example, incidence table of adverse events in the LTE period.
2. Placebo-controlled and LTE period. All the data in the placebo-controlled and LTE periods will be included in these analyses. For example, mean plot of actual laboratory values in the placebo-controlled and LTE period.
3. Placebo-controlled and LTE active treatment period. Active treatment period is defined as the study period(s) that a subject is assigned to aducanumab. For early start subjects – subjects who are assigned to aducanumab in both placebo-controlled and LTE period, all the data (placebo-controlled and LTE periods) will be included in the analyses. For late start subjects – subjects who are assigned to aducanumab in the LTE period, only data in the LTE period will be included. For example, incidence table of adverse events in the placebo-controlled and LTE active treatment period.

Subjects to be included in a certain output is determined by both the analysis population and the analysis period. For example, the incidence table of adverse events in the LTE period will include subjects in the safety population for the LTE period, i.e., all randomized subjects who received at least one dose of study treatment in the LTE period. The incidence table of adverse events in the placebo-controlled and LTE active treatment period will include subjects in the safety population for the active treatment period, i.e., all randomized subjects who received at least one dose of study treatment in the active treatment period. In this SAP we do not separately define the analysis population in each analysis period.

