3.5.2 Clinical Adverse Events

Treatment-emergent AEs (TEAEs)

All AEs will be analyzed based on the principle of treatment emergence. A treatment-emergent AE was defined as an AE that started or worsened after the start of first infusion of study treatment.

To define treatment emergence for AEs with missing start or stop date or time the following additional criteria will be used:

- if both the start and stop dates for a particular AE are missing, then that AE is considered treatment emergent;
- if the start date for a particular AE is missing and the stop date/time falls after the first dose date/time, then that AE is considered treatment emergent;
- if the start date for a particular AE was the same as the first dose date, and the start time was missing, then that event is considered treatment emergent.

For AEs with a partial start date, the year/month of the event date will be compared to that of the first dosing date to determine whether the event is treatment emergent.

In addition, SAEs that occurred since a subject was screened in the study and prior to the first infusion of study treatment, which by definition are not treatment-emergent, will be analyzed separately.

Only TEAEs will be included in the AE tables, unless otherwise specified. Listings of AEs will include all events, whether treatment-emergent or not.

As specified in the protocol, subjects were expected to return to the study site for an End of Study visit 18 weeks after the last administration of study treatment. However, some subjects may elect to continue study participation on a modified schedule after discontinuing treatment, possibly in substantial excess of 18 weeks. For most general AE summaries, AEs with an onset more than 18 weeks after the last dose will be excluded (will specify in the footnote of the specific table). For incidence rate analyses excluding AEs more than 18 weeks after the last dose, the “last day on study” in follow-up time calculation will be replaced with

“18 weeks after last dose or last day on study, whichever earlier”. Summaries of deaths and AEs leading to study withdrawal, and other selected analyses will include all AEs regardless of the time since the last dose. Listings will include all AEs, unless otherwise specified.

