3.5.3.5 Time to event analysis

Kaplan-Meier plot of time to first ARIA-E event will be produced based on safety MRI data for the placebo-controlled and LTE active treatment period. Only ARIA-E events that occurred during this period will be included. Time to event is calculated as date of the MRI assessment that initially detects the ARIA-E event - date of the first active infusion +1. Censor time for subjects without ARIA-E is calculated as date of the last MRI assessment in the study - date of the first active infusion +1. Estimated proportion with ARIA-E and number of subjects at risk at selected timepoints will also be presented. The plot will be presented by LTE treatment group stratified by ApoE status.

CONFIDENTIAL

The information contained herein may not be used, disclosed, or published without the written consent of Biogen MA Inc.

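### The exposure-adjusted ARIA-E rate runs to the last MRI with no limit tied to the last dose, so it is a rate over MRI follow-up and can understate on-drug risk

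*SAP*

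**What the plan says.** LTE SAP 3.5.3.4 defines the time at risk. For subjects with an event, "The exposure adjusted follow-up time is from the first active dose until the initial occurrence of ARIA-E for those who experienced ARIA-E". For subjects without one, "the day of the last MRI assessment in the placebo-controlled and LTE active treatment period will be used as the end of follow-up". Placebo-controlled SAP 4.5.3.4 is parallel: "the day of the last MRI assessment in the placebo-controlled period will be used as the end of follow-up".

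The period named in the LTE rule is defined in LTE SAP 3.1.2: "Active treatment period is defined as the study period(s) that a subject is assigned to aducanumab". It does not end when dosing ends.

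The Kaplan-Meier plot in LTE SAP 3.5.3.5 censors event-free subjects at "date of the last MRI assessment in the study - date of the first active infusion +1". Placebo-controlled SAP 4.5.3.5 uses the last MRI in the placebo-controlled period. None of these four sections links the end of follow-up to the last dose.

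The adverse event sections (4.5.2, and 3.5.2 in the LTE SAP) do make that link. They note that "some subjects may elect to continue study participation on a modified schedule after discontinuing treatment, possibly in substantial excess of 18 weeks". Most general adverse event summaries then leave out events starting more than 18 weeks after the last dose. Incidence rates that exclude such events end follow-up at "18 weeks after last dose or last day on study, whichever earlier". Deaths, events leading to withdrawal and some further analyses, not named, keep all events.

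**The concern.** ARIA-E is the adverse event of special interest, and a reader will take an exposure-adjusted rate as the rate of ARIA-E while exposed to aducanumab. The SAP recognises that subjects may stay on study long after stopping drug and limits follow-up for that reason in one family of rates. It sets no such limit for ARIA-E.

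If event-free subjects go on having MRIs long after their last dose, that time enters the denominator. If ARIA-E is rarer then, the rate falls below the on-drug rate, and falls further in a group with more event-free stoppers who stay in follow-up. Two dose groups with the same on-drug risk could then show different rates. Section 3.5.3.4 summarises dosing history only for subjects who had ARIA-E, so that section would not show how much event-free time was off drug.

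**Working it through.** The SAP states no ARIA-E rate, stopping rate or amount of off-drug MRI time, so there is no figure of its own to reproduce.

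**Inputs**
- c = 18/52 = 0.346 years: the SAP's own 18-week limit.
- H = horizon: 1.5 years (Week 78), 3 years, and 6.5 years (338/52, the last LTE efficacy visit).
- λ = 0.15 per year until 18 weeks after the last dose, then zero: assumption.
- θ = stopping rate = -ln(0.70)/1.5 = 0.238 per year. The 30% is the drop-out rate in the sample size section, used only as an anchor.
- r = share of stoppers who keep having MRIs, 0.25 to 1: assumption.

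**Formulas** (mean years per subject, k = λ + θ, L = H - c)
- Event-free time up to the 18-week cap: A = (1 - e^(-λc))/λ + e^(-λc)(1 - e^(-kL))/k.
- Later event-free MRI time, if every stopper who stays is followed to H: B = r θ e^(-λc) [L/k - (1 - e^(-kL))/k²].
- Events per subject = λA. Planned rate = λA/(A + B); capped rate = λA/A = λ. Shortfall = B/(A + B).

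At H = 1.5 and r = 1: A = 1.221, B = 0.130, shortfall 0.130/1.351 = 9.6%, so a true 15 per 100 person-years is shown as 13.5.

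The later horizons depend on who is followed. Case 1 follows every staying stopper to H. Case 2 assumes that those who stop before Week 78 do not enter the LTE and end at Week 78, or at 18 weeks off drug if later. B is then summed over stopping times up to 1.5 - c with end 1.5, and from 1.5 to H - c with end H.

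| H (years) | A | B, case 1 (r = 0.25 to 1) | Shortfall, case 1 | B, case 2 (r = 0.25 to 1) | Shortfall, case 2 |
|---|---|---|---|---|---|
| 1.5 | 1.221 | 0.033 to 0.130 | 3-10% | same | 3-10% |
| 3 | 1.911 | 0.145 to 0.580 | 7-23% | 0.051 to 0.203 | 3-10% |
| 6.5 | 2.560 | 0.555 to 2.219 | 18-46% | 0.236 to 0.943 | 8-27% |

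**Comparisons between groups**, with the same formulas and λ = 0.20, r = 0.5:
- Dose groups stopping at 0.12 and 0.30 per year, 3 years: 18.6 v 16.7 per 100 person-years in case 1; 19.5 v 18.7 in case 2. Capped: 20 v 20.
- Early start (4.5 years) v late start (3 years), stopping 0.20 per year: 16.3 v 17.7 in case 1; 18.5 v 17.7 in case 2. The sign changes.

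**If off-drug hazard is not zero.** A simulation of 100,000 subjects per scenario used a constant on-drug hazard of 0.10 per year, 1.5 years of MRIs after stopping, and stopping rates of 0.05, 0.15 and 0.30 per year. The ratio of planned to capped rate was:
- no hazard off drug: 0.95, 0.87, 0.78;
- half the on-drug hazard: 0.98, 0.94, 0.89;
- equal hazard: 1.00 throughout.

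With MRIs ending 18 weeks after the last dose, the ratio is 1.00 in every scenario. With a front-loaded hazard (0.50 per year for 9 months, then 0.05), the ratio is 0.98, 0.93 and 0.86 even when stopping does not change the hazard, because the added time falls late.

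**Kaplan-Meier** (stopping 0.30 per year, 1.5 years of MRIs, no off-drug hazard), planned v capped:
- constant hazard: 12.5% v 14.0% at 1.5 years, 31.1% v 39.1% at 5 years;
- front-loaded: 32.6% v 33.9%, and 40.6% v 44.8%.

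The relative loss is 1.5/14.0 = 11% and 8.0/39.1 = 20% with constant hazard, and 1.3/33.9 = 4% and 4.2/44.8 = 9% when front-loaded, against 22% for the rate in both. With equal hazard off drug the curve is unchanged.

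**The case against.** A reader might infer that ARIA-E risk is understated as planned. The documents do not support that. The SAP says that subjects may stay on a modified schedule; it does not say that MRIs continue on it, and the visit schedule is in the protocol, which is not at hand. Nor does it say that ARIA-E is rarer after stopping. Both conditions are needed.

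A reader might also infer that the SAP contradicts itself. It does not. Both SAPs openly define this type of rate as running to the end of follow-up. The 18-week rule covers most general adverse event summaries, not all, and other analyses may keep every event. ARIA-E has its own population and data source. Late ARIA-E events are not cut either, so numerator and denominator match. This stands: the planned rate is valid for what it measures.

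Three further points stand. A subject who stops because of a first ARIA-E adds no off-drug time, since the clock stops at the event, so more stopping in a group does not by itself dilute its rate. The larger figures need early stoppers to have MRIs for years. A claim that early start would look better than late start cannot be kept, because its direction depends on who is followed.

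Finally, incidence proportions from both data sources are also reported, and these sections plan no test or decision on the rate. That limits the consequences, but it does not make the label accurate.

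**Conclusion.** The point holds in a limited form. The text fixes a rate over all MRI follow-up in an assigned period and calls it exposure adjusted, while the same SAPs cap other rates at 18 weeks after the last dose. It can understate on-drug ARIA-E risk, on two conditions that the SAP neither shows nor rules out: MRIs more than 18 weeks after the last dose in event-free subjects, and a lower hazard then.

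The size rests wholly on the assumed hazard, stopping rate and share staying. Within the placebo-controlled period it is modest; it becomes large only over a long LTE with continued MRIs off drug. The Kaplan-Meier curve is a separate and smaller matter. This is an inexpensive improvement to make before the rates are read as on-drug risk, not an error that invalidates the planned analysis.

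**What to change.** In 4.5.3.4 and in LTE 3.5.3.4, add beside the planned rate an ARIA-E rate that ends event-free time at the earlier of the last MRI and 18 weeks after the last dose, and counts only ARIA-E first seen by that date. Add a matching supportive Kaplan-Meier plot in 4.5.3.5 and LTE 3.5.3.5. Keep the uncapped rate and plot, label that rate as adjusted for MRI follow-up, and list every ARIA-E first seen after the cut-off so that none is hidden.

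The cost is a short addition to each SAP, one derived date in the programs, and one more table and plot per SAP. Censoring soon after treatment stops may be informative if stopping is related to ARIA-E risk, which is why both versions should be shown. If off-drug MRI time proves negligible, they will agree.

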3.5.3.5 Time to event analysis

Kaplan-Meier plot of time to first ARIA-E event will be produced based on safety MRI data for the placebo-controlled and LTE active treatment period. Only ARIA-E events that occurred during this period will be included. Time to event is calculated as date of the MRI assessment that initially detects the ARIA-E event - date of the first active infusion +1. Censor time for subjects without ARIA-E is calculated as date of the last MRI assessment in the study - date of the first active infusion +1. Estimated proportion with ARIA-E and number of subjects at risk at selected timepoints will also be presented. The plot will be presented by LTE treatment group stratified by ApoE status.

CONFIDENTIAL

The information contained herein may not be used, disclosed, or published without the written consent of Biogen MA Inc.

3.5.4 Clinical Laboratory Data

The following clinical laboratory parameters are assessed in the protocol and will be analyzed:

- Hematology:
 - White blood cells (leukocytes), lymphocytes, neutrophils, monocytes, eosinophils, basophils
 - Red blood cells (erythrocytes), erythrocytes distribution width, erythrocytes mean corpuscular volume, erythrocytes mean corpuscular hemoglobin, erythrocytes mean corpuscular hemoglobin concentration
 - Hemoglobin
 - Hematocrit
 - Platelet count
- Blood chemistry:
 - Liver: alanine aminotransferase (ALT), aspartate aminotransferase (AST), alkaline phosphatase (ALP), total bilirubin, direct bilirubin, gamma-glutamyl-transferase (GGT)
 - Renal: blood urea nitrogen (BUN), creatinine
 - Electrolytes: sodium, potassium, chloride, bicarbonate
 - Other: glucose, calcium, phosphorus, albumin, uric acid, lactate dehydrogenase (LDH), total protein
- Urinalysis: specific gravity, potential of hydrogen (pH), color, blood, glucose, ketones, protein, white blood cells, red blood cells

3.5.4.1 Quantitative analyses

For numeric laboratory parameters, actual values will be summarized by visit for all the visits in the placebo-controlled and LTE period. Number of evaluable subjects, mean, standard deviation, median, 25% and 75% quartiles, minimum and maximum values will be presented at each visit.

Plots of mean actual values (with standard error) for numeric laboratory parameters at each visit for all the visits in the placebo-controlled and LTE period will be provided.

Summary of change from baseline and percent change from baseline for numeric laboratory parameters will be done on the placebo-controlled and LTE active treatment period. Placebo-controlled baseline will be used for early start subjects and LTE baseline will be used for late start subjects. Change and percent change from baseline will be calculated based on the LTE baseline for late start subjects. Number of evaluable subjects, mean, standard deviation, median, 25% and 75% quartiles, minimum and maximum values will be presented at each visit.

Listings of individual laboratory measurements by patients for all the parameters will be provided.

Visit windows for by visit summaries

For laboratory by visit summaries, the analysis visit should be defined using visit windows (see Table 5 below). If there is more than 1 value in the same analysis visit window for a certain parameter for a subject, then the closest record to the target visit day will be used for the by visit analysis. If there are 2 values in the same analysis visit window with the same distance from the target visit day for a certain parameter for a subject, then the record with the later date will be used for the by visit analysis. If there are 2 values on the same day for a certain parameter for a subject, then the record with the later time will be used for the by visit analysis.

Table 5: Visit Windows for Laboratory by Visit Summaries

Analysis visit	Analysis visit window ¹	
	For subjects who received the first dose of aducanumab in the placebo-controlled period	For subjects who received the first dose of aducanumab in the LTE period
Baseline	Last value prior to the first dose of aducanumab	Last value prior to the first dose of aducanumab
Week 24	[2, 252]	[2, 252]
Week 48	[253, 420]	[253, 420]
Week 72	[421, 525]	[421, 588]
Week 78	[526, end day of the placebo-controlled period ²]	NA
Week 104	[start day of the LTE period ³ , 812]	[589, 868]
Week 128	[813, 980]	NA
Week 152	[981, 1148]	[869, 1246]
Week 176	[1149, 1428]	NA
Week 232	[1429, 1806]	[1247, 1708]
Week 284	[1807, 2170]	≥ 1709
Week 336	≥2171	NA

1. Visit windows are defined based on days relative to the first dose of aducanumab.
2. The end day of the placebo-controlled period is the last day before the first infusion in LTE, or the last day in study for subjects who do not enter LTE.
3. The start day of the LTE period is the day of first infusion in LTE period.

3.5.4.2 Qualitative analyses

For qualitative analyses, all values will be included (not just the “analyzed record” within each visit window in the quantitative analyses).

Shift analyses

Laboratory data will be summarized using shift tables where appropriate for the placebo-controlled and LTE active treatment period. Each subject's hematology, blood chemistry and urinalysis numeric values will be flagged as "low", "normal", or "high" relative to the normal ranges of the central laboratory or as "unknown" if no result is available. Each subject's urinalysis categorical values will be flagged as "positive" or "negative", or "unknown" if no value is available.

Shifts from baseline to high/low status will be presented for hematology, blood chemistry and urinalysis numeric parameters, and shifts from baseline to abnormal (positive) will be presented for urinalysis categorical parameters. Shift to low includes normal to low, high to low, and unknown to low; Shift to high includes normal to high, low to high, and unknown to high. Subjects need to have at least one post-baseline evaluation and a baseline value not low or high or positive (including missing) in order to be included in the analysis.

For early start subjects, the placebo-controlled baseline will be used and shifts that occurred in either placebo-controlled or LTE period will be included. For late start subjects, the LTE baseline will be used and shifts that occurred in the LTE period based on LTE baseline will be included.

Grade analyses

Worst post-baseline grade will be summarized for each laboratory parameter in both exclusive way and cumulative way for the placebo-controlled and LTE active treatment period. Subjects need to have at least one post-baseline evaluation in the active treatment period in order to be included in the analysis. Common Toxicity Criteria for Adverse Events v4.0.3 (CTCAE) published on 2010-06-14 will be used for grade determination. Grade determination is based solely on laboratory values not taking AEs into account.

Potentially Clinically Significant laboratory abnormalities analyses

Please refer to the placebo-controlled SAP for the parameters and criteria for potentially clinically significant laboratory abnormalities analyses.

The number of subjects with potentially clinically significant laboratory abnormalities post-baseline will be summarized for the placebo-controlled and LTE active treatment period.

Subjects need to have at least one post-baseline evaluation in the active treatment period and a baseline value not potentially clinically significant (including missing) in order to be included in the analysis.

Same as the shift analysis, for early start subjects, the placebo-controlled baseline will be used and abnormalities that occurred in either placebo-controlled or LTE period will be included. For late start subjects, the LTE baseline will be used and PCS abnormalities that occurred in the LTE period based on LTE baseline will be included.

Potential serious hepatotoxicity

In this SAP, we define potential serious hepatotoxicity as ALT or AST > 3x ULN and total bilirubin > 2x ULN at any time post-baseline in the placebo-controlled and LTE active

CONFIDENTIAL

The information contained herein may not be used, disclosed, or published without the written consent of Biogen MA Inc.

treatment period (not necessarily concurrent). A scatterplot of the maximum post-baseline ALT or AST value relative to ULN and maximum post-baseline total bilirubin value relative to ULN (not necessarily concurrent) for each subject will be provided. A line plot of ALT, AST, ALK and total bilirubin values over time in the active treatment period for subjects with potential serious hepatotoxicity will be provided. In addition, subjects with ALT > 1x ULN, >3x ULN, >5x ULN, >10x ULN or >20x ULN, subjects with AST > 1x ULN, >3x ULN, >5x ULN, >10x ULN or >20x ULN, subjects with total bilirubin >1x ULN or >2x ULN, subjects with ALP >1x ULN or >1.5x ULN, and subjects with AST or ALT > 3x ULN post-baseline accompanied by concurrently elevated total bilirubin >1.5x ULN or > 2x ULN in the active treatment period will be presented. Concurrent is defined as on the same day. A listing of subjects with potential serious hepatotoxicity will be provided.

